# 11 Insurance

The sponsor will appropriately ensure the study; trial will be covered in accordance to medical centers requirements and local regulation.

# 12 Data Collection, Processing and Statistical Analysis

# 12.1 Data Collection and Processing

# 12.1.1 Subject Data Protection

Investigators are responsible for keeping a list of all subjects, including subject numbers, full names and last known addresses, identification log. Throughout the study, all collected data will be identified by subject number only and kept in accordance with local data protection requirements and with regulation (EU) 2016/679 of the European parliament and of the council of 27 April 2016 on the protection of natural persons with regard to the processing of personal data and on the free movement of such data and repealing Directive 95/46/EC (General Data Protection Regulation) GDPR.

# 12.2 Statistical Analysis and Sample Size

# **12.2.1 Sample Size Consideration**

The rationale for the sample size of 10 subjects for this FIH trial is based on regulatory requirements set down by the FDA in the Keratoprosthesis 510K guidance document and on a clinical trial for corneal blindness using a KPro- trial number NCT03126903 running currently (A Clinical Study to Evaluate the KeraKlear Keratoprosthesis in Patients With Corneal Opacity). In the KearKlear FIH trial 15 patients were included and followed up for 7-21 months. The FDA 510k demands 20 patients followed up for approximately one year. (press here for the FDA protocol)

 A new epidescemetic keratoprosthesis: pilot investigation and proof of concept of a new alternative solution for corneal blindness.Br J Ophthalmol. 2015 Nov;99(11):1483-7. doi: 10.1136/bjophthalmol-2014-306264. Epub 2015 Apr 13.Alio JL, Abdelghany AA, Abu-Mustafa SK, Zein G.

**CONFIDENTIAL** - THIS DOCUMENT CONTAINS CONFIDENTIAL AND PROPRIETARY INFORMATION. THIS DOCUMENT MAY NOT BE REPRODUCED, USED, OR DISCLOSED TO ANY THIRD PARTY WITHOUT PRIOR WRITTEN CONSENT.

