# 3 Study Synopsis

# Study Name:

Prospective, open label, single arm, First in Human clinical study to assess Safety and efficacy of the CorNeat Keratoprosthesis for the treatment of corneal blindness

**Objectives**: The objective of this clinical study is to prove the safety of the CorNeat Keratoprosthesis (KPro).

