# Sample size consideration:

Sample size of 10 patients for FIH study to assess the safety of the application on a nonstatistical basis According to FDA guidance document for Keratoprosthesis, a sample size of 20 patients is required for product 510(k) approval Guidance dated March 3, 1999

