# 5 Study Objectives And Endpoints

# 5.1 Objective

The objective of this clinical trial is to prove the safety and efficacy of the CorNeat KPro device intra and post-operatively.

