### 12.2.2 Sample Size Justification

Reference to FDA guidance for Keratoprosthesis 510K where proving safety is the target and 20 subjects with a minimum of 330 days of follow up is needed.

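### The protocol rests its sample size of 10 on guidance it says needs 20 subjects and a precedent of 15, while its objectives claim to prove safety

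*Protocol*

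**What the plan says.** On the basis for 10, Protocol section 12.2.1 states: "The rationale for the sample size of 10 subjects for this FIH trial is based on regulatory requirements set down by the FDA". It adds a second basis, a clinical trial of another keratoprosthesis. The figures in the same paragraph are 20 for the guidance ("The FDA 510k demands 20 patients followed up for approximately one year") and 15 for that device's first-in-human trial ("15 patients were included and followed up for 7-21 months").

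Section 12.2.2, headed as the justification, consists of one sentence pointing to the guidance, "where proving safety is the target and 20 subjects with a minimum of 330 days of follow up is needed". The sample size justification in the synopsis (section 3) repeats it.

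The sample size consideration in the synopsis differs. It presents 10 as a first-in-human number for assessing safety on a non-statistical basis, and says "a sample size of 20 patients is required" for 510(k) approval.

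On the goal, the synopsis says: "The objective of this clinical study is to prove the safety of the CorNeat Keratoprosthesis (KPro"). Section 5.1 goes further: "to prove the safety and efficacy of the CorNeat KPro device intra and post-operatively". The primary safety endpoint (synopsis and section 5.2.1) asks that event frequency and severity up to 12 months be lower than under standard of care, with section 10.8 as the reference. Section 12.2.3 says that no statistical methods are applied and no separate SAP is in use.

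**The concern.** A section that justifies a sample size should lead to that number. Here both cited sources lead elsewhere, and the one quoted in section 12.2.2 ties 20 subjects to the very goal the objectives adopt, proof of safety. On the protocol's own account, the trial claims that goal with half the subjects its cited source needs. For the efficacy part of section 5.1, no size rationale is offered at all.

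At stake is what the completed trial may be said to show. Section 4.2.4 makes the wider indications follow once safety has been validated in a limited study under the guidance, and section 4.2.9 bases the FDA submission on that guidance. The protocol does not say that this trial alone is that study. But with section 12.2 citing the guidance as the basis for 10, and the objectives speaking of proof, an ethics committee, the DSMB or a later reader could take ten uneventful subjects as meeting a standard that the same document puts at twenty.

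**Working it through.** **Can 10 be reproduced?** The protocol gives no alpha, power, margin or effect size, so there is no power calculation to rerun. The only inputs offered are the two sources in section 12.2.1.

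- Guidance: 20. Difference from plan: 20 − 10 = 10; ratio 10/20 = one half.
- Comparator first-in-human trial: 15. Difference from plan: 15 − 10 = 5.

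Neither gives 10, and no reduction from 20 or 15 is described. Follow-up is not the shortfall: the 12-month visit has a 14-day window (section 8.1.6), so its earliest date is about 365 − 14 = 351 days, above the 330 quoted. The number of subjects is the shortfall.

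**What can 10 subjects show?** The confidence level is an assumption here, because the protocol states none. For 0 events in n subjects the exact upper bound is 1 − 0.05^(1/n) (one-sided 95%) or 1 − 0.025^(1/n) (two-sided 95%).

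| n | One-sided 95% upper bound | Two-sided 95% upper bound |
|---|---|---|
| 10 | 1 − 0.05^(1/10) = 25.9% | 1 − 0.025^(1/10) = 30.8% |
| 20 | 1 − 0.05^(1/20) = 13.9% | 1 − 0.025^(1/20) = 16.8% |

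**Set against the reference rates in section 10.8.** The smallest n for which zero events puts the one-sided bound below a rate p is ln(0.05)/ln(1 − p), rounded up.

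| Reference rate | n needed, with zero events | P(0 events in 10) at that rate, (1 − p)^10 |
|---|---|---|
| Corneal melt, up to 30% | 9 | 2.8% |
| Endophthalmitis, upper end 11.4% | 25 | 29.8% |
| Loss of retention at 1 year, 6% | 49 | 53.9% |
| Endophthalmitis, lower end 1.2% | 249 | 88.6% |

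If the true one-year loss of retention equalled the 6% reference, ten subjects would show no loss 53.9% of the time. A clean result is therefore no evidence of a rate below 6%. With 20 subjects it would still occur 0.94^20 = 29.0% of the time, so the cited standard does not supply that proof either.

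At the high end, 0/10 does fall below 30% on the one-sided bound (25.9%), but not on the two-sided bound (30.8%). If the true melt rate were 15%, an assumed halving, 0/10 would occur with probability 0.85^10 = 19.7%.

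**The case against.** The best defence is the synopsis. Its sample size consideration already calls 10 a non-statistical first-in-human number and assigns 20 to 510(k) approval. The title and section 6 speak of assessing safety and efficacy, which suggests that *prove* is loose drafting. The analysis is listings, counts and percentages, so no test or success threshold depends on N. The figure of 20 is disclosed in four places, and the protocol nowhere says that 10 satisfies it. *Based on* may mean no more than informed by.

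Much of this stands. It rules out three stronger readings that a reader might infer:

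- **That the guidance is the only basis given for 10.** The synopsis gives another.
- **That the protocol falsely claims compliance with the guidance.** It makes no such statement. The text is a non sequitur set beside openly reported figures. The guidance itself was not available for this review, so whether it allows a smaller first cohort is unknown.
- **That 10 is too few and must become 20.** Zero-event bounds show that 10 is small, which a first-in-human design accepts, and the bounds for 20 would not support proof against the lower reference rates.

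The defence does not remove the conflict. The synopsis qualifier is absent from section 12.2, where the rationale formally sits. The synopsis justification that follows it reverts to the 20-subject statement. Both objectives still say *prove*, and the primary safety endpoint still asks for rates below standard of care. Leaving the matter to an SAP is not an answer either: objectives and size rationale are protocol content, and section 12.2.3 says no separate SAP is in use.

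**Conclusion.** The point holds as an internal inconsistency in the rationale and the stated claim, not as a fault in the choice of 10. Sections 12.2.1 and 12.2.2 and the synopsis justification support 10 with figures of 20 and 15. They conflict with the synopsis sample size consideration, and the objectives promise proof that the design cannot give. On the protocol's own account the trial has half the subjects its cited source asks for when safety is to be proved. Zero events in 10 leaves true rates up to 25.9% (one-sided) or 30.8% (two-sided) compatible with the data, against a reference as low as 6% for one-year loss of retention.

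This rests on the protocol's description of the guidance and on an assumed 95% confidence level; the shortfall of 10 against 20 and 15 depends on neither bound. The fault should be fixed because it governs what may be concluded, but it changes no procedure, endpoint assessment or patient number and need not hold up the trial.

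**What to change.** Leave N at 10 and amend the wording.

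1. **Rationale (sections 12.2.1 and 12.2.2, synopsis justification).** Carry over the basis in the synopsis sample size consideration. Say that 10 is a first-in-human feasibility size, not derived from the guidance or the comparator trial, and that this trial alone does not meet the 20-subject standard.
2. **Precision (section 12.2).** State what 10 subjects give, for example that 0/10 events leaves an exact 95% upper bound of 25.9% one-sided or 30.8% two-sided, and name the confidence level chosen.
3. **Objectives (synopsis and section 5.1).** Replace *prove* with *assess* or *describe*, and use the same scope in both places: initial safety, device retention and visual acuity, so that both effectiveness endpoints stay covered.
4. **Primary safety endpoint (synopsis and section 5.2.1).** Present the comparison with standard of care as descriptive. Otherwise the overclaim survives the change to the objectives.

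The cost is one written amendment with EC/REB approval (section 12.5), with no extra patients, visits or data. The downside for the sponsor is a less favourable stated claim.

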### 12.2.2 Sample Size Justification

Reference to FDA guidance for Keratoprosthesis 510K where proving safety is the target and 20 subjects with a minimum of 330 days of follow up is needed.

### 12.2.3 Statistical Analysis

There is not a separate Statistical Analysis Plan (SAP) document in use for the trial since no statistical methods are applied in this study.

The safety analysis set will consist of all patients who were enrolled into the study. Individual listings of adverse events including adverse events (reported term), duration, relationship to the study device, severity and the adverse events outcome will be provided for the total population, where applicable. AEs will be summarized using frequency counts and percentages.

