#### Statistical considerations

Statistical calculations are not required in this FIH study

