# 5.2 Endpoints

# 5.2.1 Primary Safety Endpoint

The frequency and severity of all unanticipated adverse device-related events (UADE) or treatment-related adverse events, during and after implantation of the CorNeat KPro device up to 12 months should be less than SOC (as detailed in section Known Potential Risks).

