# 5.2.2 Effectiveness Endpoints:

Primary Effectiveness Endpoint: Device retention Secondary Effectiveness Endpoint: Improvement in visual acuity

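### The protocol promises proof and a comparison with standard-of-care rates, yet applies no statistical methods; about 10 eyes reported as point percentages cannot support that comparison

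*Protocol*

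**What the plan says.** On methods, section 12.2.3 states that there is no separate SAP, the reason being that "no statistical methods are applied in this study". The synopsis, under Statistical considerations, says: "Statistical calculations are not required in this FIH study". The synopsis also gives the basis of the sample size: "Sample size of 10 patients for FIH study to assess the safety of the application on a nonstatistical basis".

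On outputs, section 12.2.3 plans individual adverse event listings (reported term, duration, relationship, severity, outcome) and adds: "AEs will be summarized using frequency counts and percentages". The synopsis and section 10.1 add tables by System Organ Class, Preferred Term, severity and relatedness.

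On aims, section 5.1 sets out to "prove the safety and efficacy of the CorNeat KPro device intra and post-operatively"; the synopsis objective likewise speaks of proving safety. Under the primary safety endpoint (section 5.2.1 and the synopsis), the frequency and severity of the listed events up to 12 months "should be less than SOC (as detailed in section Known Potential Risks"). Section 5.2.2 gives "Primary Effectiveness Endpoint: Device retention", with improvement in visual acuity as the secondary effectiveness endpoint. Neither has a stated summary.

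On populations, section 12.2.3 defines the safety set as everyone enrolled. Section 7.4 names an ITT cohort that includes dropouts and a second cohort that excludes them. Section 8.1.4 records a failed procedure as an operative failure.

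**The concern.** A protocol would normally be allowed to leave analysis detail to its SAP. Here it says that none is in use, so the statement has to be read as the plan.

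The plan then pulls in two directions. Proving safety and being below standard of care are comparative claims against numbers. Section 10.8 supplies those numbers: 6% device loss at one year, melt up to 30%, retroprosthetic membranes 27 to 47.6%, endophthalmitis 1.2 to 11.4%. No method is given for the comparison and no measure of uncertainty is planned, so anyone applying the criterion as written has only point percentages from about 10 eyes. For the two effectiveness endpoints not even a percentage is specified.

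What is at stake is the wording of the conclusion. Under section 10.10 a DSMB reviews the data of the first 10 implanted subjects, and its conclusions go to the sponsor, the REB and the health ministry. A low percentage could be reported there as meeting the primary safety criterion when the data would also be compatible with rates well above the benchmark.

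**Working it through.** The plan's own figure is n = 10, declared non-statistical. It has no alpha, power, margin or precision behind it, so there is no calculation to reproduce. The check is what 10 eyes can show.

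**Inputs.** n = 10 subjects, taken as one operated eye each (synopsis; section 7.1). Benchmarks p from section 10.8. The interval level is not in the protocol; two-sided 95% exact (Clopper-Pearson) is assumed, with one-sided 95% as a variant.

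**Step 1: precision.**
- 0/10 events: upper limit = 1 − 0.025^(1/10) = 30.8%. One-sided 95%: 1 − 0.05^(1/10) = 25.9%.
- 1/10 events: 0.3% to 44.5%.
- The same for retention: 10/10 kept has a lower limit of 69.2%; 9/10 has 55.5% to 99.7%.

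So zero events does not bring the two-sided upper limit below 6%, 11.4% or 30%. It does fall below the highest figures in section 10.8, namely 38% (upper end for raised intraocular pressure) and 47.6% (upper end for membranes). The one-sided limit of 25.9% also falls below 27% and 30%, but not below 11.4% or 6%.

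**Step 2: an assumed decision rule.** Suppose the criterion were read as: observed x/10 strictly below p. For a device whose true rate equals p, the chance of meeting it is the binomial sum of C(10,x) p^x (1−p)^(10−x) over all x with x/10 < p.

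| Benchmark (section 10.8) | p | Counts that meet the rule | Chance when the true rate is p |
|---|---|---|---|
| Corneal melt, stated maximum | 30% | 0 to 2 | 0.028 + 0.121 + 0.233 = 38% |
| Membranes, lower end | 27% | 0 to 2 | 47% |
| Membranes, upper end | 47.6% | 0 to 4 | 44% |
| Endophthalmitis, lower end | 1.2% | 0 | 0.988^10 = 89% |
| Endophthalmitis, upper end | 11.4% | 0 or 1 | 0.298 + 0.384 = 68% |
| Device loss at one year, if used for retention | 6% | 0 | 0.94^10 = 54% |

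Several benchmarks are ranges, and the protocol does not say which end applies. For endophthalmitis the answer moves from 68% to 89% on that choice alone.

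**Step 3: scale.** To exclude 6% loss with no losses observed, n must satisfy 0.94^n ≤ 0.05, so n ≥ ln 0.05 / ln 0.94 = 48.4, that is 49 eyes (60 at one-sided 97.5%). This shows only how far 10 eyes are from such a claim; it does not argue for a larger study.

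**The case against.** The best reply is that this is a single-arm first-in-human study, openly sized on a non-statistical basis. It needs no powered test, and descriptive reporting is a legitimate choice. With 10 subjects the per-subject listings are the main evidence, any reader can derive an exact interval from x/10, and Kaplan-Meier would add little to a list of removal times. Oversight rests on DSMB review (section 10.10) and a stopping rule that counts patients (section 10.11), not on percentages against a benchmark. All of that stands, and neither the sample size nor the absence of a hypothesis test is criticised here.

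Three stronger readings are tempting, and the documents do not support them:

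- *That percentages are the only planned summary of adverse events.* Listings and tables by class, term, severity and relatedness are planned too.
- *That subjects who leave early are counted as event-free.* No section says so. Section 7.4 plans a cohort that excludes dropouts beside the ITT cohort, and safety follow-up of dropouts where possible. What is missing is which analysis uses which cohort.
- *That 0/10 losses is the success rule for retention and 1/10 a failure.* The retention endpoint has no threshold, and section 10.8 is tied only to the safety endpoint, which speaks of frequency and severity together with no event-by-event rule. The step 2 probabilities therefore describe an assumed rule.

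What the reply does not answer is that a purely descriptive study should not carry a primary endpoint worded as a comparison and an objective worded as proof.

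**Conclusion.** The point holds in a limited form. The protocol disclaims statistical methods in sections 3 and 12.2.3 while sections 3, 5.1 and 5.2.1 state aims that need at least a measure of uncertainty, and it states no summary for retention or visual acuity. This is a conflict within the current text, not detail left for later.

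Its size: about 31 percentage points of uncertainty remain even with no events in 10, and the true rate could be as high as 44.5% after one event. The 38%, 68% and 54% figures depend on reading the criterion as an observed percentage below a single benchmark. Replacement of dropouts under section 7.4 could raise the number implanted a little without changing the conclusion.

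It is a should-fix: it affects what may be concluded, not the conduct of the trial or the data collected.

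**What to change.** 1. In section 12.2.3 and in the synopsis under Statistical considerations, replace the statements that no methods or calculations apply. Changing only one would leave the two in conflict.
2. Report month-12 retention, and each complication with a rate in section 10.8, as x/n with an exact 95% interval in one named population. Reconcile that population with the enrolled set (12.2.3), the ITT and dropout-excluded cohorts (7.4) and operative failures (8.1.4), and say how an operative failure counts for retention.
3. List follow-up time and time to removal per subject, and show the dropout-excluded results alongside, so that incomplete follow-up is visible.
4. List BCVA at screening and month 12 per subject, in categories where acuity is non-numeric, since inclusion requires only light perception (7.2.1.7).
5. Reword the objective (synopsis, 5.1) and the primary safety endpoint (synopsis, 5.2.1) so that the standard-of-care rates are descriptive context beside the intervals, not a conclusion drawn from the point estimate.

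The cost is a paragraph in section 12.2.3, matching edits in the synopsis and section 5, and little analysis work. No visits, subjects or data are added. The downside for the sponsor is that wide intervals will stand beside favourable percentages.

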#### 7.4 Replacement of Dropouts

Subjects have the right to withdraw from the study at any time, for any reason, without jeopardizing their medical care. Subjects, who have not completed the 6-month follow-up visit and drop out of the study for any reason, may be replaced. Dropouts will be evaluated in the Intent to Treat (ITT) Cohort. A separate cohort will exclude these subjects. Every effort will be made to determine the reason for the subject dropping out of the study. Where possible, subjects will be followed for safety and encouraged to return for follow-up visits for any unresolved safety events.

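### The 12-month safety comparison rests on crude percentages with no allowance for incomplete follow-up, so a subject lost before an event counts as event-free

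*Protocol*

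**What the plan says.** Section 5.2.1 sets a time-bound criterion: the frequency and severity of unanticipated device-related or treatment-related events "during and after implantation of the CorNeat KPro device up to 12 months should be less than SOC", with section 10.8 (Known Potential Risks) as the reference.

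Section 12.2.3 gives the whole analysis. On the set: "The safety analysis set will consist of all patients who were enrolled into the study". On the summary: "AEs will be summarized using frequency counts and percentages". On anything further: "There is not a separate Statistical Analysis Plan (SAP) document in use for the trial since no statistical methods are applied in this study". The point therefore cannot be left to a later document.

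Section 7.4 foresees early departure: "Subjects, who have not completed the 6-month follow-up visit and drop out of the study for any reason, may be replaced". It keeps dropouts in an intent-to-treat cohort, plans a second cohort without them, and asks that they be followed for safety as far as possible. Section 8.1.2 makes the day of implantation the day of enrolment, so a subject enters the denominator at surgery. The synopsis describes the sample size as "Sample size of 10 patients for FIH study to assess the safety of the application on a nonstatistical basis".

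**The concern.** The criterion concerns risk over a fixed 12 months, but the planned figure is a percentage over whatever follow-up each subject happened to have. An event after last contact is not counted, while the subject still counts in full in the denominator. This applies to losses before or after month 6, replaced or not. It also applies if the trial is stopped under section 10.11, where further follow-up is decided patient by patient.

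The error has one direction: towards a lower rate and an easier pass. Section 5.2.1 compares bare figures, without interval or test, so a small shift can change the reading. In addition, three sets coexist (the safety set, the intent-to-treat cohort and the cohort without dropouts), and the protocol does not say which one supplies the figure to be compared with 10.8.

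**Working it through.** The protocol states no expected rate, dropout figure or computed precision, so there is no figure of its own to reproduce. The check asks how far the crude percentage would fall short.

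**Direction.** For a given set of enrolled subjects, those with an event seen before last contact are a subset of those who would have one by month 12, and the denominator is the same. The crude percentage is therefore at most the full-follow-up percentage, and equal to it only if no event is missed.

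**Inputs from the protocol.** 10 subjects; 12 months of follow-up; 6% loss of retention at 1 year (10.8); corneal melt up to 30% (10.8, no time point given).

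**Assumptions.** 10 completers; k = 1 to 3 dropouts, each replaced; exit at month 3; constant hazard; exit unrelated to events; no events captured after exit; 30% treated as a 12-month risk.

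**Formulae.** Risk seen in a dropout: q = 1 − (1 − p)^(3/12). Expected crude rate with replacement: (10p + kq)/(10 + k). Without replacement: ((10 − k)p + kq)/10.

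For p = 0.30, q = 1 − 0.70^0.25 = 0.0853. For p = 0.06, q = 1 − 0.94^0.25 = 0.0154.

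| True risk | k | With replacement | Without replacement |
|---|---|---|---|
| 30% | 1 | (3 + 0.0853)/11 = 28.0% | (2.7 + 0.0853)/10 = 27.9% |
| 30% | 2 | (3 + 0.1706)/12 = 26.4% | (2.4 + 0.1706)/10 = 25.7% |
| 30% | 3 | (3 + 0.2559)/13 = 25.0% | (2.1 + 0.2559)/10 = 23.6% |
| 6% | 1 | (0.6 + 0.0154)/11 = 5.6% | (0.54 + 0.0154)/10 = 5.6% |
| 6% | 2 | (0.6 + 0.0307)/12 = 5.3% | (0.48 + 0.0307)/10 = 5.1% |
| 6% | 3 | (0.6 + 0.0461)/13 = 5.0% | (0.42 + 0.0461)/10 = 4.7% |

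The shortfall is never smaller without replacement, because replacement lowers the dropouts' share of the denominator from k/10 to k/(10 + k).

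**Sensitivity.**
- With exit anywhere from month 0 to month 6 and replacement, a true 30% appears as 27.3–28.8% (k = 1), 25.0–27.7% (k = 2) and 23.1–26.8% (k = 3).
- If 70% of events fall in month 1, exit at month 3 with k = 3 still gives 28.3%.
- For losses spread over months 6 to 12, which are not replaced, a true 30% appears as 29.3%, 28.7% and 28.0% for k = 1, 2, 3.

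**Does censoring repair it?** In 10,000 simulated trials per setting, with exit uniform over months 0 to 6 and unrelated to events, a true 30% gave crude means of 28.1%, 26.0% and 24.1% at dropout probabilities of 10%, 20% and 30%. The Kaplan-Meier means were 30.1%, 30.1% and 30.2%.

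**Effect on a bare comparison.** Three melts among ten fully followed subjects is 3/10 = 30%, not below 30%. Add one subject lost before any of these events and the crude figure is 3/11 = 27.3%, which passes. Kaplan-Meier still gives 30%, since all three events occur with ten at risk at the start and no further censoring.

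**Precision for scale.** The exact 95% interval for 3/10 is 6.7% to 65.2%. For 0/10 the upper limit is 30.8%. At a true 6%, the chance of no event in 10 is 0.94^10 = 0.54.

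**The case against.** The strongest reply is that the effect is conditional and minor. It vanishes if nobody leaves, or if the safety follow-up asked for in 7.4 captures later events. The study is declared descriptive and lists adverse events individually, and the exact interval at 10 subjects dwarfs a shortfall of a few points. Nothing in the documents supports two or three dropouts in particular. All of this stands, and it limits the weight of the point. It does not supply a rule for incomplete follow-up, and 5.2.1 compares figures without an interval.

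Three stronger readings are tempting but not supported:

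- A reader might infer that replacing dropouts causes the bias. It slightly dilutes it (26.4% against 25.7% for k = 2 at a true 30%). The cause is the crude percentage with incomplete follow-up.
- A reader might infer that short-follow-up subjects are never removed from any analysis. Section 7.4 plans a cohort that excludes dropouts. That cohort is no full repair: it discards events they had before leaving and is unbiased only if leaving is unrelated to events. The gap is that no set is assigned to 5.2.1.
- A reader might take the melt figure (up to 30%) and the membrane figure (up to 47.6%) as 12-month comparators. Section 10.8 gives no time point for either. Of the figures used here, only the 6% loss of retention is stated at 1 year. Nor do the documents give onset times for melt or membrane that would show most events falling after dropout.

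**Conclusion.** The point holds in conditional form. The only planned summary cannot deliver a 12-month risk when follow-up is incomplete, and its error runs only towards meeting the criterion. Neither an SAP nor an assigned cohort closes the gap.

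Under the stated assumptions, the expected shortfall for one to three replaced dropouts leaving at month 3 is about 2 to 5 percentage points at a true 30%, and 0.4 to 1.0 points at a true 6%. It is zero without loss of observation. The number and timing of dropouts, the constant hazard and the 12-month reading of the 30% are assumptions, not protocol figures. The shortfall is small beside the sampling uncertainty, so this is a low-cost improvement to the analysis text and not a threat to the study as a whole.

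**What to change.** Amend 12.2.3 in one paragraph:

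- State that the 5.2.1 comparison uses all subjects in whom implantation was attempted, and what role the two cohorts in 7.4 then have.
- Keep the crude counts and percentages.
- Beside them, give the 12-month cumulative incidence of first event (Kaplan-Meier), censored at last safety contact.
- Show the number still under observation at months 6 and 12 next to each percentage.

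Section 10.6 already records event onset. It does not record last contact, which has to come from the visit records. The censored estimate assumes that loss is unrelated to the event, and the numbers under observation let the reader judge how much rests on that.

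The cost is a slightly less favourable and less simple figure. If every subject is observed to month 12, the result does not change.
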